6.3. Handling of Dropouts or Missing Data

Last-observed-value-carried forward (LOCF) (for categorical variables) and MMRM (for continuous variables) will be the primary methods used to handle missing data. Nonresponder imputation (NRI) will also be used as a supplementary analysis method for categorical data. The censoring rules along with their associated estimator assumptions are described in Sections 6.3.1 through 6.3.3.

As efficacy and health outcome data can accrue after a patient permanently discontinues study drug, general censoring rules to the data will be applied to all efficacy and health outcome observations subsequent to these events.

The censoring rule will censor efficacy and health outcome results after permanent study drug discontinuation. This censoring rule will be applied to all continuous and categorical efficacy and health outcome endpoints. Sections 6.3.1 through 6.3.3 summarize the imputation methods for the various efficacy and health outcome endpoints.

6.3.1. Last Observation Carried Forward

Categorical data will primarily be imputed by carrying forward the last post-baseline assessment for the measure. According to ICH E9 R1, the while-on-treatment strategy could be applied based on the last post-baseline value (scheduled or unscheduled visits) at or before the visit of interest while the patient was still on study drug. Patients in the analysis population without at least 1 postbaseline observation will be defined as non-responders for this analysis. After last observation carried forward (LOCF) imputation is applied, data from patients with nonmissing baseline and at least 1 postbaseline observation will be included in the analyses. These LOCF analyses help ensure the maximum number of randomized patients who were assessed post-baseline will be included in the analyses.

All categorical endpoints will utilize LOCF methodology after censoring efficacy and health outcome results for those who permanently discontinued study drug. For all patients who permanently discontinue study treatment or discontinue from the study for any reason at any time, the last nonmissing postbaseline observation on or prior to discontinuation will be carried forward to subsequent time points for evaluation. If a patient does not have a nonmissing observed record (or one imputed by other means) for a postbaseline visit prior to discontinuation, the last postbaseline record prior to the missed visit will be used for the visit.

Further, all continuous primary and secondary efficacy and health outcome variables will be imputed using LOCF as a supplementary analysis.

6.3.2. Mixed Model for Repeated Measures

For the continuous primary, secondary, and exploratory efficacy and health outcome variables, such as ALP and Itch NRS, MMRM analyses will be performed to mitigate the impact of missing data. This approach assumes that missing observations are missing-at-random (missingness is related only to observed data and not to any unobserved data) during the study and takes into account both the missingness of data and the correlation of the repeated

measurements. An MMRM method can be justified based on the hypothetical strategy (ICH E9 R1) for handling intercurrent events.

All continuous endpoints will utilize MMRM after censoring efficacy and health outcome results for those who permanently discontinued study drug.

6.3.3. Nonresponder Imputation

For the analysis of all categorical efficacy and health outcome variables, the nonresponder imputation (NRI) method will be used as a supplementary analysis. NRI can be justified based on the composite strategy (ICH E9R1) for handling intercurrent events. In this strategy a patient is defined as a responder only if (i) they meet the clinical requirements for response at the predefined time and (ii) they remain on the assigned study treatment. Failing either criteria by definition makes them a non-responder.

All secondary categorical endpoints will utilize the NRI method after censoring efficacy and health outcome results for those who permanently discontinued study drug. Patients in the analysis population without at least 1 post-baseline observation will also be defined as nonresponders for all visits. As well, patients who are missing a value prior to discontinuation (ie, the patient is missing an intermediate visit) will be imputed as nonresponders at that visit.

6.4. Multicenter Studies

This study will be conducted by multiple investigators at multiple sites internationally. However, since the number of patients at each site is expected to be very small, no further sensitivity analysis will be performed for the sites or countries.

6.5. Multiple Comparisons/Multiplicity

No multiplicity adjustment will be used in this study.

6.6. Patient Disposition

An overview of patient populations will be summarized by treatment group. Frequency counts and percentages of patients excluded prior to randomization by primary reason for exclusion will be provided for patients who failed to meet study entry requirements during screening.

Patient disposition through Week 12 will be summarized using the mITT population. Frequency counts and percentages of patients who complete the study treatment visits or discontinue early from the study along with whether they completed follow-up or did not complete follow-up will be summarized separately by treatment group for patients along with their reason for study discontinuation. Frequency counts and percentages of patients who complete the treatment or discontinue treatment early will also be summarized separately by treatment group for patients along with their reason for treatment discontinuation.

A listing of patient disposition will be provided for all randomized patients, with the extent of their participation in the study and the reason for discontinuation. A listing of all randomized patients with their treatment assignment will also be provided.

6.7. Patient Characteristics

Patient characteristics including demographics and baseline characteristics will be summarized descriptively by treatment group for the mITT population. Historical illnesses and pre-existing conditions will be summarized descriptively by treatment group for the safety population. Descriptive statistics including number of patients (n), mean, SD, minimum, 1st quartile, median, 3rd quartile, and maximum will be provided for continuous measures, and frequency counts and percentages will be tabulated for categorical measures. A listing of patient demographics will also be provided for the mITT population. No formal statistical comparisons will be made among treatment groups unless otherwise stated.

[Table JAIV.6.1](#) describes the specific variables and how they will be summarized.

Table JAIV.6.1. Patient Characteristics

Variable	Continuous measure Summary	Categorical Summary
Age ^a	Yes	None
Sex	No	Male, Female
Race	No	American Indian/Alaska Native, Asian, Black/African American, Native Hawaiian or other Pacific Islander, White, or Multiple
Geographic region	No	By Country
Height (cm)	Yes	None
Weight (kg)	Yes	None
BMI ^b	Yes	<18.5 kg/m ² , ≥18.5 and <25 kg/m ² , ≥25 and <30 kg/m ² , ≥30 and <35 kg/m ² , ≥35 and <40 kg/m ² , ≥40 kg/m ²
Alcohol use	No	Never, Current, Former
Tobacco use	No	Never, Current, Former
Age at PBC diagnosis (years) ^c	Yes	<18 years, ≥18 years
Duration of PBC diagnosis ^d	Yes	0 to <2 years, 2 to <5 years, 5 to <10 years, 10 to <20 years, ≥20 years
Current UDCA use	No	Yes, No
Baseline ALP level	Yes	Baseline ALP ≤2.5xULN, Baseline ALP >2.5xULN
Quality of Life for Primary Biliary Cirrhosis (PBC-40) at baseline	Yes	None
Functional Assessment of Chronic Illness Therapy-Fatigue (FACIT-F) at baseline	Yes	None
Itch Numeric Rating Scale (NRS) at baseline	Yes	No pruritus (0), Mild pruritus (>0 to <4), Moderate pruritus (≥4 to <7), Severe pruritus (≥7 to <9), Very severe pruritus (≥9) Frequency table for each value
Fatigue NRS	Yes	None
Physician's Global Assessment of Disease Activity at baseline	Yes	None
Total bilirubin at baseline	Yes	None

Abbreviations: ALP = alkaline phosphatase; BMI = body mass index; NRS = Numeric Rating Scale; PBC = primary biliary cholangitis; UDCA = ursodeoxycholic acid.

^a Age in years will be calculated as (number of months between first dose date and July 1st of birth year) / 12, and truncated to a whole-year (integer) age.

^b Body Mass Index (BMI) will be calculated as: $BMI (kg / m^2) = Weight (kg) / (Height (m))^2$.

^c Age at diagnosis in years will be calculated as (number of months between date of PBC diagnosis and July 1st of birth year) / 12, and truncated to a whole-integer age.

^d The duration of PBC from diagnosis (year) = [(Date of informed consent – Date of PBC diagnosis) + 1] / 365.25. If year of onset is missing, duration of PBC will be set as missing. Otherwise, unknown month will be taken as January, and unknown day will be taken as 01. The duration of PBC will be rounded to 1 decimal place.

6.7.1. Historical Illness and Pre-existing Conditions

Historical illnesses are defined as those conditions recorded in the Pre-existing Conditions and Medical History electronic case report form (eCRF) or from the Prespecified Medical History: Comorbidities eCRF with an end date prior to the informed consent date. The number and percentage of patients with selected historical diagnoses will be summarized by treatment group using the safety population. Historical diagnoses will be categorized using the Medical Dictionary for Regulatory Activities (MedDRA[®], most current available version) algorithmic standardized MedDRA queries (SMQs) or similar pre-defined lists of preferred terms (PTs) of interest.

Pre-existing conditions are defined as those conditions recorded in the Pre-existing Conditions and Medical History eCRF, the Prespecified Medical History: Comorbidities eCRF, or the Adverse Events eCRF with a start date prior to the date of informed consent and an end date on or after informed consent or no end date (that is, the event is ongoing). For events occurring on the day of the first dose of study treatment, the date and time of the onset of the event will both be used to determine if the event was pre-existing. Conditions with a partial or missing start date (or time if needed) will be assumed to be “not pre-existing” unless there is evidence, through comparison of partial dates, to suggest otherwise. Pre-existing conditions will be categorized using the MedDRA SMQs or similar pre-defined lists of PTs of interest. Frequency counts and percentages of patients with selected pre-existing conditions will be summarized by treatment group using the safety population. If a preexisting condition worsens in severity on or after date of first dose of study treatment, it will be considered a TEAE from the date of worsening onwards.

6.8. Treatment Compliance

Compliance with investigational product treatment for baricitinib and placebo will be assessed through counts of returned investigational product tablets. A patient will be considered significantly noncompliant if he or she misses more than 20% of the prescribed doses during the study, unless the patient’s investigational product was withheld by the investigator for safety reasons.

Similarly, a patient will be considered significantly noncompliant if he or she is judged by the investigator to have intentionally or repeatedly taken more than the prescribed amount of medication.

$$\text{Compliance} = \frac{\text{total number of tablets dispensed} - \text{total number of tablets returned}}{\text{expected number of total tablets}}$$

where

- Total number of tablets dispensed: sum of tablets dispensed in the period of interest prior to Visit x ;
- Total number of tablets returned: sum of the tablets returned in the period of interest prior to and including Visit x ;

- Expected number of tablets: number of days in the period of interest*number of tablets taken per day = [(date of visit – date of first dose + 1) – number of days of temporary drug interruption]*number of tablets taken per day

Descriptive statistics for percent compliance and non-compliance rate will be summarized for the mITT population by treatment group for Week 0 through Week 12. Sub-intervals of interest, such as compliance between visits, may also be presented. The number of expected doses, tablets dispensed, tablets returned, and percent compliance will be listed by patient for Week 0 through Week 12.

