Treatment comparisons of continuous efficacy and health outcome variables will be made using mixed-effects models for repeated measures (MMRM) with treatment, [REDACTED]

[REDACTED] An unstructured covariance matrix will be used to model the within-patient variance-covariance errors. Type III sums of squares for the least-squares (LS) means will be used for the statistical comparison and the 90% confidence interval (CI) will also be reported. Treatment group comparisons with placebo at Week 12 and other visits will be tested.

Treatment comparisons of categorical efficacy variables will be made using a logistic regression analysis with treatment, cohort, baseline ALP ($\leq 2.5X$ ULN, $>2.5X$ ULN) and baseline UDCA use (yes/no) in the model. The proportions and 90% CI will be reported.

2. Schedule of Activities

Table JAIV.1. Schedule of Activities for Cohorts A and B

Procedure	Screening		Treatment Period						Follow-up
	V1 (up to 49 days prior to V3)	V2 (at least 4 weeks after V1)	V3 ^a Week 0	V4 Week 1 (±2 days)	V5 Week 4 (±4 days)	V6 Week 8 (±4 days)	V7 Week 12 (±4 days)	ET	V801 28 days post last dose (±4 days)
Informed consent	X								
Inclusion and exclusion criteria review	X		X						
Patient demography	X								
Physical examination ^b	X								
Pre-existing conditions and medical history (includes substance usage) ^c	X								
Randomization			X						
Investigational product dispensed			X		X	X			
Investigational product returned and compliance assessed				X	X	X	X	X	
Study Procedures									
TB test ^d	X								
Read PPD if applicable (48-72 hours post PPD)	X ^e								
Chest x-ray ^f	X								
ECG ^g	X								
AE/SAE review	X		X	X	X	X	X	X	X
Concomitant medication review	X		X	X	X	X	X	X	X
Symptom-directed physical examination			X	X	X	X	X	X	X
Targeted event history ^h			X	X	X	X	X	X	X
Vital signs (blood pressure, pulse, and temperature)	X		X	X	X	X	X	X	X
Waist circumference			X				X	X	

Procedure	Screening		Treatment Period						Follow-up
	V1 (up to 49 days prior to V3)	V2 (at least 4 weeks after V1)	V3 ^a Week 0	V4 Week 1 (±2 days)	V5 Week 4 (±4 days)	V6 Week 8 (±4 days)	V7 Week 12 (±4 days)	ET	V801 28 days post last dose (±4 days)
Height			X						
Weight			X	X	X	X	X	X	X
Itch NRS	X		X	X	X	X	X	X	X
PBC-40	X		X	X	X	X	X	X	X
FACIT-F	X		X	X	X	X	X	X	X
Fatigue NRS	X		X	X	X	X	X	X	X
Physician Global Assessment	X		X	X	X	X	X	X	X
QIDS-SR ¹⁶			X	X	X	X	X	X	
Laboratory Tests									
FSH ⁱ	X								
TSH	X								
Serum pregnancy test ^j	X								

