5.2. Number of Participants

Approximately 52 subjects are planned to be randomized in this study. Approximately 12 patients will receive baricitinib 2-mg, approximately 20 patients will receive baricitinib 4-mg, and approximately 20 patients will receive placebo.

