7.5. Treatment Compliance

Patient compliance with study medication will be assessed at Visit 4 through Visit 7 and at Early Termination during the treatment period by counting returned tablets and direct questioning. Deviation(s) from the prescribed dosage regimen should be recorded in the electronic case report form (eCRF).

The patient will be considered significantly noncompliant if he or she misses more than 20% of study medication during the study, unless the patient’s investigational product was withheld by the investigator for safety reasons. Similarly, a patient will be considered significantly noncompliant if he or she is judged by the investigator to have intentionally or repeatedly taken more than the prescribed amount of medication.

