8.1.2. Permanent Discontinuation from Study Treatment

Possible reasons leading to permanent discontinuation of investigational product:

- **Subject Decision**
 - the patient requests to discontinue investigational product.
- **Investigator Decision**
 - the investigator decides that the patient should be discontinued from investigational product
- **Discontinuation due to a hepatic event or liver test abnormality:** Patients who are discontinued from investigational product because of a hepatic event or liver test abnormality should have additional hepatic safety data collected via eCRF. Details on continued hepatic monitoring are provided in Section 9.4.7.

If multiple values are obtained during screening, the highest value prior to receipt of investigational product will be used as baseline. Discontinuation of the investigational product for abnormal liver tests **should be** considered by the investigator when a patient meets one of the following conditions after consultation with the Lilly designated medical monitor:

- a. For patients with **baseline normal ALT and/or AST**, the following will result in discontinuation:

single laboratory test	ALT or AST >8 x ULN
single laboratory test	ALT or AST >3 x ULN and TBL >2 x ULN or International Normalized Ratio (INR) >1.5
single laboratory test	ALT or AST >3 x ULN with the appearance of fatigue, nausea, vomiting, right upper-quadrant pain or tenderness, fever, rash, and/or eosinophilia (>5%)
confirmed laboratory test (2 tests)	ALT or AST >2 x ULN and no other known cause.
during temporary interruption of IP	ALT or AST >5 x ULN for more than 2 weeks after temporary interruption of investigational product

- b. For patients with **baseline elevated ALT and/or AST**, the following will result in discontinuation:

confirmed laboratory test (2 tests)	ALT >5 x baseline, or >400 U/L (whichever occurs first)
confirmed laboratory test (2 tests)	ALT >3 x baseline and TBL >2 x ULN or INR >1.5
confirmed laboratory test (2 tests)	ALT >3 x baseline with appearance of severe fatigue, nausea, vomiting, right upper-quadrant abdominal pain, fever, rash, and/or eosinophilia (>5%)
confirmed laboratory test (2 tests)	ALT or AST >2 x ULN and no other known cause
confirmed laboratory test (2 tests)	TBL >1.5 x baseline upon retesting and no other known cause
during temporary interruption of IP	ALT >4 x baseline or >300 U/L (whichever occurs first) for more than 2 weeks after temporary interruption of investigational product

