10.3.2.4. Treatment Compliance

Treatment compliance with the randomly assigned study medication will be evaluated at every clinic visit through the counts of returned investigational product tablets. A patient will be considered significantly noncompliant if he or she misses more than 20% (i.e., compliance <80%) of the prescribed doses during the study, unless the patient's investigational product is withheld by the investigator for safety reasons. Similarly, a patient will be considered significantly noncompliant if he or she is judged by the investigator to have intentionally or repeatedly taken more than the prescribed amount of medication.

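### The SAP 6.8 compliance denominator runs to the visit date and removes only temporary interruptions, so days after a permanent stop are scored as missed doses

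*SAP*

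**What the plan says.** SAP 6.8 defines compliance as tablets dispensed minus tablets returned, divided by expected tablets. Expected tablets are days in the period of interest times tablets per day. The SAP then sets this equal to an explicit expression whose day count is "date of visit – date of first dose + 1) – number of days of temporary drug interruption". Temporary interruption is the only subtraction.

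The significantly noncompliant label goes to a patient who, in the words of Protocol 10.3.2.4, "misses more than 20% (i.e., compliance <80%) of the prescribed doses during the study". SAP 6.8 exempts a patient whose product was "withheld by the investigator for safety reasons". Protocol 7.5 and 10.3.2.4 give the 20% rule but no denominator of their own.

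Under Protocol 7.5, compliance "will be assessed at Visit 4 through Visit 7 and at Early Termination during the treatment period by counting returned tablets". Protocol 8.1.2 treats permanent discontinuation separately from the interruptions in 8.1.1. One of its listed reasons is that "the patient requests to discontinue investigational product". The Schedule of Activities (Protocol Section 2) gives ET no timing of its own, but sets the follow-up visit at "28 days post last dose (±4 days").

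Percent compliance and the noncompliance rate are summarized by arm for the mITT population, and percent compliance is listed by patient. SAP 6.15 names compliance below 80% as a potential example of a protocol deviation.

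**The concern.** After a permanent stop no doses are prescribed, so none can be missed. The formula still counts those days as expected dosing days, up to the visit at which compliance is assessed. A patient who took every prescribed tablet can therefore be reported as partly adherent.

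The formula also disagrees with SAP 6.13.1, which ends exposure at the last dose. The two sections can give one patient different numbers of treatment days.

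At stake are the arm-level compliance summary, the patient listing and, for some patients, an unwarranted candidate for deviation review. Arms of about 12 and 20 are small enough for one patient to show in the summary.

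**Working it through.** SAP 6.8 gives no worked compliance figure to reproduce, so the check applies its formula directly.

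**Inputs**
- Denominator and 80% threshold: SAP 6.8.
- Tablets per day: 2 in Cohort A, 1 in Cohort B (Protocol Table JAIV.3). They multiply numerator and denominator alike and cancel.
- Arm sizes: about 12 on 2 mg; for the higher dose, "approximately 20 patients will receive baricitinib 4-mg" (Protocol 5.2).
- Follow-up visit: 28 ± 4 days after the last dose (Protocol Section 2).
- Gap g from the decision to stop to the visit: **assumed**, because the documents give none.

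**Formula.** Take the first dose on day 0 and n daily doses, all taken, so the last dose is on day n−1. Let the decision to stop fall on that day and the visit g days later, with all unused tablets returned.

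Expected days = (n−1+g) − 0 + 1 = n+g, so compliance = n/(n+g).

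| n | g | Calculation | Compliance |
|---|---|---|---|
| 28 | 0 | 28/28 | 100% |
| 28 | 7 | 28/35 | 80.0% (not below threshold) |
| 28 | 8 | 28/36 | 77.8% |
| 28 | 14 | 28/42 | 66.7% |
| 56 | 7 | 56/63 | 88.9% |
| 56 | 14 | 56/70 | 80.0% (not below threshold) |
| 56 | 15 | 56/71 | 78.9% |

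**When the score falls below 80%.** n/(n+g) < 0.80 means n < 0.80n + 0.80g, so g > n/4. That is more than 7 days after 28 doses, or more than 14 days after 56. This applies to a patient who took every dose. A patient who missed a few needs a smaller gap: at 95% adherence over 28 days, a 7-day gap gives 95% × 28/35 = 76.0%.

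**Bound on the gap.** ET stands before the follow-up visit in the schedule, and that visit falls at most 28 + 4 = 32 days after the last dose. At that outer limit a 28-dose patient would score 28/60 = 46.7%.

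**Arm level, one patient affected.** One spurious label moves the noncompliance rate by 1/20 = 5.0 points (4 mg) or 1/12 = 8.3 points (2 mg). One score of 66.7% instead of 100% lowers the arm mean by 33.3/20 = 1.7 or 33.3/12 = 2.8 points.

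**Comparison within the SAP.** The patient with n = 28 and g = 14 has 28 exposure days under SAP 6.13.1 and 42 expected dosing days under SAP 6.8.

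**The case against.** **The period of interest could be read as ending with treatment.** The term is not defined elsewhere, and the label refers to prescribed doses. But the SAP equates the period with the visit-date expression, so a programmer following the text would use the visit date.

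**The safety provisions protect many early stoppers.** This stands for the label. A stop led by the investigator for safety should be exempt, and recorded hold days before the stop are already subtracted. The exemption does not alter the percentage, and on its wording it does not reach a patient who simply asks to stop.

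**Not every day between last dose and ET is miscounted.** This also stands. If a patient lapses and announces the decision only at ET, doses were still prescribed until then and were properly missed. The gap must run from the decision to stop, not from the last dose.

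**A reader could see the cause of a low score.** In part. The compliance listing shows expected doses, tablets dispensed and tablets returned, and under SAP 6.6 "patients who complete the treatment or discontinue treatment early will also be summarized separately by treatment group". The summary percentages would still be wrong.

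**A reader might infer that the gap has no limit**, because ET is untimed. The documents do not support that: as scheduled, ET precedes a visit anchored to the last dose.

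**Conclusion.** The rule is wrong as written, and the matter is minor. Percent compliance is understated for any permanent stop followed by a gap before the visit. For a patient who took every dose, a spurious label below 80% can arise only if the stop was not for safety and the gap exceeds a quarter of the days dosed.

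The size rests on assumed gaps and on the number of early stops, neither of which the documents give. If ET falls on the day of the decision, there is no effect.

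A reader might infer that adherent early stoppers will generally be flagged, or that efficacy conclusions are affected. Neither follows. The label is confined as above, and SAP 6.15 offers the 80% cut as a potential example, leaves importance to team review and refers to a separate document. No per-protocol set is defined. The mITT population and the primary ALP analysis do not use compliance, so the effect is confined to the compliance summary, the listing and possible deviation review.

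**What to change.** Add one sentence to SAP 6.8: the expected-tablet period ends at the earlier of the visit date and the recorded date of permanent treatment discontinuation, with the last dose date used only if no discontinuation date is recorded.

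The patient with 28 doses who decides to stop on the last-dose day then scores 28/28 = 100% whatever the gap. The discontinuation date is the better first choice because it still counts a patient's own lapse. With doses on days 0 to 27, a lapse on days 28 to 48 and a decision on day 48, it gives 28/49 = 57.1%; a last-dose cut-off would give 28/28 = 100%.

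The cost is that sentence and a small programming change. The documents reviewed do not show the case report form field, but the censoring rule in SAP 6.3 already needs to know when study drug was permanently stopped, so new data collection is unlikely. The fallback date is already used in SAP 6.13.1.
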